8.9 Pregnancy Test

A serum hCG will be performed at the Screening Visit for all WCBP. If performed within 24 hours before the Screening Visit, a historical serum hCG test can be used. A urine pregnancy test will be performed at subsequent visits as indicated in Appendix A.

8.10 Vital Signs

Vital signs will be collected as indicated in Appendix A. Vital signs will include temperature, heart rate, respiratory rate, blood pressure, and SpO₂. For outpatients, pulse oximeters, thermometers, and blood pressure cuffs will be provided for home use.

8.11 Electrocardiograms

ECGs should be performed 2 hours (\pm 30 minutes) after the first study drug administration on Day 1 and 2 hours (\pm 30 minutes) after the morning dose on Day 4 and Day 7. ECGs may be performed at any time at subsequent visits. ECGs will be collected as indicated in Appendix A. Patients should be in a supine position for at least 10 minutes prior to ECG measurement.

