7.1.4 Exploratory Endpoints

Exploratory endpoints will include the change from baseline (pre-dose on Day 1) in biomarkers related to pulmonary inflammation, fibrosis and/or lung injury at Day 7, Day 14, Day 28, and Day 60, including but not limited to the following, with each dose (Phase 2) or the optimal dose (Phase 3) of FP-025 compared to placebo:

- MMP-12, MMP-7, and MMP-9;
- Transforming growth factor- β ;
- Connective tissue growth factor;
- C-reactive protein (CRP);
- Cytokines (IFN- γ , tumor necrosis factor [TNF]- α , IL-6, IL-1 β , and C-C motif chemokine ligand 2 [monocyte chemoattractant protein-1]);
- Ferritin;
- Released N-terminal pro-peptide of type III collagen;
- Internal epitope in the 7S domain of type IV collagen;
- C-terminal of released C5 domain of type VI collagen $\alpha 3$ chain (endotrophin);
- Neo-epitope of MMP-2, 9, and 13-mediated degradation of type I collagen;
- Neo-epitope of MMP-2, 9, and 12-mediated degradation of type IV collagen;
- Neo-epitope of MMP-2-mediated degradation of type VI collagen;
- Neo-epitope of MMP-1 and 8-mediated degradation of CRP; and
- Neo-epitope of plasmin-mediated degradation of cross-linked fibrin.

Additional biomarkers not listed here may be evaluated at a future date.

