8 SAFETY ASSESSMENTS

8.1 Adverse Events

An AE is defined as any untoward medical occurrence in a clinical investigation patient administered a pharmaceutical product, which does not necessarily have a causal relationship with this treatment. An AE can therefore be any unfavorable and/or unintended sign (including an abnormal laboratory finding), symptom, or disease temporally associated with the use of an investigational medicinal product, whether or not related to the investigational medicinal product. All AEs, including observed or volunteered problems, complaints, or symptoms, are to be recorded on the appropriate eCRF.

AEs will be monitored and recorded from the time of the first dose of study drug (Day 1 [Visit 2]) until the end of the study (Day 60). All events occurring prior to the first dose of study drug will be recorded as medical history. Patients should be instructed to report any AE that they experience to the Investigator, whether or not they think the event is due to study treatment. Beginning at Day 1 (Visit 2), Investigators should make an assessment for AEs at each visit and record the event on the appropriate AE eCRF.

Wherever possible, a specific disease or syndrome rather than individual associated signs and symptoms should be identified by the Investigator and recorded on the eCRF. However, if an observed or reported sign or symptom is not considered a component of a specific disease or syndrome by the Investigator, it should be recorded as a separate AE on the eCRF. Additionally, the condition that led to a medical or surgical procedure (eg, surgery, endoscopy, tooth extraction, or transfusion) should be recorded as an AE, not the procedure itself.

Any medical condition already present prior to the first dose of study drug should be recorded as medical history and not be reported as an AE unless the medical condition or signs or symptoms present at baseline changes in severity, frequency, or seriousness at any time during the study. In this case, it should be reported as an AE.

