Clinically significant abnormal laboratory or other examination (eg, electrocardiogram [ECG]) findings that are detected during the study or are present at the Day 1 (Visit 2) and significantly worsen during the study should be reported as AEs, as described below. The Investigator will exercise his or her medical and scientific judgment in deciding whether an abnormal laboratory finding or other abnormal assessment is clinically significant. Clinically significant abnormal laboratory values occurring during the study will be followed until repeat tests return to normal, stabilize, or are no longer clinically significant. Abnormal test results that are determined to be an error should not be reported as an AE. Laboratory abnormalities or other abnormal clinical findings (eg, ECG abnormalities) should be reported as an AE if any of the following are applicable:

- If an intervention is required as a result of the abnormality;
- If action taken with the study drug is required as a result of the abnormality; or
- Based on the clinical judgment of the Investigator.

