8.8 Clinical Laboratory Assessments

Samples for blood chemistry and hematology will be obtained as indicated in Appendix A. See Appendix B for a complete list of analytes. If any additional laboratory evaluations are performed for standard of care, these data should be entered into the eCRF. If a blood chemistry or hematology assessment was performed within 24 hours prior to the first dose of study drug, it is not necessary to repeat the assessment on Day 1. Effort should be made to obtain blood chemistry and hematology at approximately the same time on each day as indicated in Appendix A; however, it should not be considered a protocol deviation if this is not possible.

Samples for urinalysis will be obtained as indicated in Appendix A. See Appendix B for a complete list of analytes.

Screening and eligibility laboratory assessments may be performed at the local laboratory. All other laboratory assessments during the study will be assessed by a central laboratory.

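### No ECG is scheduled or collected before the first dose, so protocol data cannot attribute early ECG changes within a patient or give an unbiased change from baseline for them

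*Combined protocol and SAP*

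**What the plan says.** Section 8.11 sets the Day 1 ECG at 2 hours (±30 minutes) "after the first study drug administration on Day 1". The Day 4 and Day 7 ECGs are also 2 hours after a dose, and later ones may be taken at any time. Footnote l of Table 2 (Appendix A) gives the same timing. The ECG row of Table 2 is blank at Screening and marked on Days 1, 4, 7, 14, 21 and 28 and at early termination. Table 3, for discharged patients, marks the day of discharge, Day 28 and early termination.

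Section 8.7 lists 12-lead ECGs as a safety endpoint. Section 9.2.2 says that safety data will be summarised by actual treatment, and defines no ECG baseline.

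Two rules in Section 8.1 bear on how an ECG finding is classified. The line between history and adverse event is the first dose: "All events occurring prior to the first dose of study drug will be recorded as medical history". Clinically significant abnormal findings, with ECG given as an example, are reportable either when they are picked up in the course of the study or when they "are present at the Day 1 (Visit 2) and significantly worsen during the study should be reported as AEs".

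**The concern.** Both rules in Section 8.1 presuppose knowledge of the patient's state before drug. For ECGs the protocol gathers none. The only tracing scheduled for the Day 1 visit comes after dosing, so in a treated patient it may already contain a drug effect. It cannot by itself separate a long-standing abnormality from a new one.

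Safety and tolerability are part of the primary objectives (Section 2.1). Section 4.3 treats adverse events as possibly drug-related unless they are clearly unrelated or another cause, such as a pre-existing condition, is clear. Section 8.1.3 asks the investigator to weigh the time sequence. Both judgements are weaker for an early ECG finding with nothing before it. The population makes the question practical: Section 3.1.1 does not exclude Grade 3 to 4 heart failure, so some patients may well enter with an abnormal ECG.

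**Working it through.** The plan gives no figure to reproduce. The check is a count, a reading of the rules side by side, and one line of algebra.

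1. **Count of ECGs before the first dose.** Section 8.11 and footnote l put the earliest tracing at 120 ± 30 minutes after dosing, that is 90 to 150 minutes (1.5 to 2.5 hours). Table 2 schedules six ECGs from Day 1 to Day 28, all on treatment. Table 3 adds only later ones. No eligibility criterion in Sections 4.1 and 4.2 uses an ECG, and no text asks for a historical one. The count is 0.

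2. **Could the blank Screening cell be a damaged table?** This is unlikely. The ECG row has the same treatment-period pattern as the PK row, which starts on Day 1. Vital signs, physical examination and laboratory rows carry an extra leading mark at Screening. Section 8.11 independently gives only post-dose timing.

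3. **How other measurements are handled.**
   - Biomarkers: the endpoint is "change from baseline (pre-dose on Day 1").
   - Chemistry and hematology: Section 8.8 waives the Day 1 sample if one "was performed within 24 hours prior to the first dose of study drug".
   - Pregnancy test: Section 8.9 accepts a serum result from the 24 hours before Screening.
   - Height and weight: footnote f of Table 2 accepts the medical record.
   - ECG: no equivalent provision.

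4. **Classifying an abnormality first seen on the 2-hour tracing.**
   - If it existed before dosing, Section 8.1 makes it medical history, reportable only if it changes.
   - If it arose after dosing, it is an adverse event when clinically significant.
   - Both limbs of the abnormal-findings rule describe it: it was detected during the study, and it was present at the Day 1 visit. The text does not say which limb governs, and no protocol-collected ECG settles the matter.

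5. **Effect on change from baseline, if the Day 1 tracing serves as baseline.** Let B be a patient's drug-free value, d₂ the drug effect at 2 hours on Day 1, and dₜ the effect at visit t. Leave out noise and the natural course, which randomization balances between arms.
   - Change from a pre-dose baseline: (B + dₜ) − B = dₜ.
   - Change from the 2-hour tracing: (B + dₜ) − (B + d₂) = dₜ − d₂.
   - Difference from placebo in raw values at visit t: mean of dₜ, because randomization balances B.
   - Difference from placebo in raw values on Day 1: mean of d₂.

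   An effect that is present at 2 hours and persists unchanged (dₜ = d₂) gives a change of zero from the 2-hour tracing, yet appears in full in the raw comparison. An effect that appears only later (d₂ = 0) is measured correctly either way.

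**The case against.** A reader might go further than the documents allow in five ways.

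- **That early changes would go unreported as adverse events.** Section 8.1 does not say so. A clinically significant abnormality on the 2-hour tracing is detected during the study and is reportable on that ground. An ECG finding is also reportable if it requires intervention, leads to action with study drug, or is so judged by the investigator. Section 4.3 leans towards relatedness. What remains is uncertainty about attribution.
- **That the ECG analysis is biased as planned.** No passage specifies an ECG change-from-baseline analysis or names the Day 1 tracing as baseline. The change-from-baseline endpoints in Sections 7.1.3 and 7.1.4 concern other measurements. The bias in step 5 is conditional on that choice.
- **That new abnormalities cannot be recognised.** Those first appearing from Day 4 onward can be compared with Day 1 in the same patient, and group effects at 2 hours can be estimated against concurrent placebo.
- **That every treated patient lacks a pre-dose ECG.** Hospital patients may well have one. The protocol simply neither requires nor records it.
- **That the 2-hour tracing sits near peak exposure.** The documents give no time of peak concentration.

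It can also be said that Section 1.4 reports no treatment-related effect in dog cardiovascular safety pharmacology, and that no formal test or eligibility criterion is shown to depend on the ECG. These points lower the stakes. They do not supply the missing reference, and no later analysis definition can create a tracing that was never collected.

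**Conclusion.** The point holds in a limited form. None of the scheduled ECGs is drug-free, so protocol data cannot tell a pre-existing abnormality from one that arose in the first 1.5 to 2.5 hours after dosing. If the Day 1 tracing is taken as the reference for worsening or as the baseline, an effect present at that time is absorbed into it. If it is not, no within-patient change from a drug-free value can be calculated at all.

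The size of any bias equals the effect at 2 hours, about which the documents give no human ECG figure, so none is put on it here. Raw comparisons with placebo at each visit are unaffected, and the reporting rule is weakened rather than void. The conclusion rests on reading Table 2 as printed, which Section 8.11 and footnote l support. It is a low-cost improvement to a named safety endpoint and does not call the trial's main comparison into question.

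**What to change.** - Define ECG baseline as the latest 12-lead ECG before the first dose.
- Record the routine hospital ECG in the eCRF where one exists, in the spirit of Section 8.8 for laboratory values. Obtain a pre-dose tracing only where there is none.
- Keep the 2-hour ECG as the first post-dose value.
- Align Section 8.1 (so that worsening in an ECG is judged against the pre-dose tracing), Section 8.11, the ECG row of Table 2 and footnote l.

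The cost is one eCRF entry per patient and an occasional extra non-invasive tracing. Dosing and eligibility do not change. The change is best made before further enrolment, because a baseline missed before the first dose can be recovered later only if a hospital tracing happens to exist.

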Foresee Pharmaceuticals, Co. Ltd. (hereafter, Foresee) is developing a potent and selective MMP-12 inhibitor, known as FP-025. FP-025 has shown preclinical efficacy in a lipopolysaccharide (LPS)-induced acute lung injury mouse model in reducing inflammatory cells in BAL fluid, as well as reducing the bronchial, arteriole, and alveolar damage and lung injury induced by LPS. In a bleomycin-induced unilateral lung fibrosis rat model, FP-025 reduced fibrosis, reduced bronchial and arterial damage in the lung, and attenuated the level of fibrotic biomarkers such as collagen 1, collagen 4, and transforming growth factor (TGF)- β 1. FP-025 has undergone repeated-dose Good Laboratory Practice (GLP) toxicity studies in 2 species (up to 28 days of dosing in rats and dogs), as well as GLP safety, pharmacology, and genotoxicity studies.

In humans, single and multiple ascending dose studies of FP-025 have been conducted in healthy human patients, demonstrating dose-proportional and time-independent pharmacokinetics (PK) up to 400 mg twice daily (BID) for 7 days. In these studies, FP-025 was safe and well tolerated. FP-025 is currently undergoing a house dust mite-induced allergen-challenge study in the Netherlands (Study FP02C-18-001). The objective of the study is to test the potential of FP-025 to reduce the late allergic response and other inflammatory biomarkers due to the allergen challenge. A dose regimen of 400 mg BID for 12 days is being used. At this time, there have been no safety issues identified in this ongoing study. All doses have been well tolerated with no deaths or treatment-emergent serious adverse events (SAEs).

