Standard of care procedures for mechanical ventilation (eg, low tidal volume protective mechanical ventilation) and standard of care procedures for weaning from mechanical ventilation will be followed. The clinical criteria for weaning readiness testing and discontinuation from mechanical ventilation are described in Appendix D.

Study drug administration will begin on Day 1 (Visit 2) following randomization. All patients will receive standard of care and/or EUA treatment for COVID-19 in addition to the study drug. Patients will continue study drug treatment BID through Day 27 and take 1 dose on Day 28. If a patient is discharged from the hospital prior to Day 28, he/she will continue treatment as an outpatient at home with his/her assigned treatment (FP-025 100 mg BID, FP-025 300 mg BID, or placebo BID) until Day 28. Dosing instructions will be provided prior to discharge. Although treatment will be identical for inpatients and outpatients, patients discharged from the hospital will follow a different Schedule of Procedures, characterized by telemedicine (or telephone, if sites and/or patients do not have video capability) visits. The End of Treatment (EOT) Visit on Day 28

will be identical for all patients (with the exception of the arterial oxygen partial pressure [PaO₂]/fractional inspired oxygen [FiO₂] ratio, performed only in patients on invasive or non-invasive ventilation) and will include a high-resolution, non-contrast CT scan, in addition to other assessments.

After treatment is completed, all patients will undergo 2 follow-up assessments during the Follow-Up Period. The first follow-up will be a telephone visit on Day 45 to assess concomitant medications, adverse events (AEs), and the NIAID 8-point ordinal scale for COVID-19 and hospitalization outcomes score. The second follow-up will be an in-person visit on Day 60 and will include a high-resolution, non-contrast CT scan and pulmonary function tests, in addition to other assessments.

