7.1.5 Pharmacokinetic Endpoint

The PK endpoint is the plasma exposure of FP-025 at each dose level. Sampling times will be as follows:

- Day 1 (Visit 2): pre-dose, 1 hour (± 10 minutes), 3 hours (± 10 minutes), and 8 hours (± 10 minutes) post the first morning dose of study drug;

Note: If the patient is randomized in the afternoon on Day 1 (Visit 2), this will be performed after the morning dose of study drug on Day 2.

- Day 4, Day 7, Day 14, and Day 21: within 1 hour (± 10 minutes) prior to the morning dose; and
- Day 28: within 1 hour (± 10 minutes) prior to the morning dose and 1 hour (± 10 minutes) post-morning dose.

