- h. A full physical examination will be performed at EOT and Day 60. A full physical examination may include assessments of general condition, skin, eyes/ears/nose/mouth/throat, neck/thyroid, chest/lungs, heart, vascular system, lymph nodes, abdomen, extremities, nervous systems/reflexes, musculoskeletal system, and spine. Telemedicine-based physical examinations will be performed at the other visits. Telemedicine-based physical examinations (if the patient and site have video capabilities) may include assessments of general condition (eg, overall appearance and patient orientation) and an assessment of the work of breathing (eg, speech cadence, lifting hands above head). If the patient or the site do not have video capabilities, the video portion of the telemedicine-based physical examination will be omitted, and the visit will be performed by phone. In this case and in lieu of the physical or video examination, clinicians will document whether the patient is having audible shortness of breath or difficulty speaking. If there are any concerns, then the patient will be instructed to call to his/her local physician or be seen at his/her local emergency department.
- i. Vital signs include temperature, heart rate, respiratory rate, blood pressure, and SpO₂. Pulse oximeters, thermometers, and blood pressure cuffs will be provided for home use.
- j. For WCBP only.
- k. Patients should be in a supine position for at least 10 minutes prior to ECG measurement.
- l. Clinical laboratory assessments include clinical chemistry, hematology, and urinalysis. See Appendix B for a list of clinical laboratory analytes.
- m. PK analysis will occur on Day 28 within 1 hour (± 10 minutes) prior to the morning dose and 1 hour (± 10 minutes) post-morning dose.
- n. The study drug (FP-025 100 mg, FP-025 300 mg, or placebo) will be administered orally as capsules BID for 28 days.
- o. PFTs will include measurement of FVC, FEV₁, FEV₁/FVC ratios, and diffusing capacity of the lungs for carbon monoxide.
- p. Inflammatory and fibrotic biomarkers assessed may include, but are not limited to, MMP-12, MMP-7, MMP-9, TGF- β , connective tissue growth factor, PRO-C3, PRO-C4, PRO-C6, reC1M, C4M, C6M, CRPM, X-FIB (D-dimer), C-reactive protein, cytokines (IFN- γ , TNF- α , IL-6, IL-1 β , and C-C motif chemokine ligand 2 [monocyte chemoattractant protein-1]), and ferritin levels in blood.

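### ECGs are dose-timed only on Days 1, 4 and 7, so a concentration-driven effect may be diluted in weeks 2 to 4 and a by-visit summary could be misread as waning

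*Combined protocol and SAP*

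**What the plan says.** Section 8.11 sets the ECG at 2 hours (±30 minutes) "after the first study drug administration on Day 1" and at the same interval "after the morning dose on Day 4 and Day 7". For later visits it says "ECGs may be performed at any time at subsequent visits". Footnote l to Table 2 in Appendix A repeats this rule. Table 2 schedules ECGs on Days 1, 4, 7, 14, 21 and 28 and at early termination.

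Discharged patients follow Table 3, which has ECGs on the day of discharge, at Day 28 and at early termination. Its footnote k covers posture only: "Patients should be in a supine position for at least 10 minutes prior to ECG measurement".

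Four other passages bear on the point:

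- **Dosing (3.1.1):** "Patients will continue study drug treatment BID through Day 27 and take 1 dose on Day 28". The Day 28 visit window in Appendix A is ±3 days.
- **PK sampling (7.1.5):** on "Day 4, Day 7, Day 14, and Day 21: within 1 hour" (±10 minutes) before the morning dose. Day 28 has a pre-dose sample and one at 1 hour post-dose.
- **Prior exposure (1.2, 5.2):** studies in healthy people "demonstrating dose-proportional and time-independent pharmacokinetics (PK) up to 400 mg twice daily (BID) for 7 days". The asthma study doses for 12 days and is ongoing and blinded.
- **Analysis (9.2.2):** 12-lead ECGs are among the safety data to be summarized. No handling of time since dose is described.

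**The concern.** The timing rule changes partway through treatment, so time on drug is confounded with time since dose. Early tracings are all taken 2 hours after a dose. Later ones may fall anywhere in the 12-hour interval, including just before the morning dose if a site takes the ECG with the Day 14 or Day 21 PK sample. If FP-025 had an ECG effect that followed plasma concentration, a table by visit could show it shrinking after Day 7 only because the sampling time had moved.

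Weeks 2 to 4 are also where the ECG data are newest, since the cited exposure stops at 7 days in healthy people and 12 days in asthma. Exposure in these patients may differ from that in healthy people and may change as organ function and co-medication change. The Phase 2 safety data go to the iDMC, which recommends the Phase 3 dose, so a weakened late ECG signal would reach that decision.

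**Working it through.** The plan gives no figure to reproduce here. The check asks how far an untimed ECG could understate a concentration-driven effect, and whether steady state is already covered.

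**Inputs from the documents.** Twice-daily dosing, so an interval of τ = 12 h. ECG at 2 h post-dose on Days 1, 4 and 7. PK described as time-independent over 7 days.

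**Assumptions, not in the documents.** One-compartment oral model, absorption half-life 0.5 h (ka = ln 2/0.5 = 1.386 per h), elimination half-life T from 3 to 24 h (k = ln 2/T), ECG effect proportional to concentration, and untimed ECGs spread evenly over the interval.

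**Formulas** (relative units):

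- Steady state at time t: C(t) = ka/(ka − k) × [e^(−kt)/(1 − e^(−kτ)) − e^(−ka·t)/(1 − e^(−ka·τ))]
- Mean over the interval: 1/(kτ)
- Day 1, 2 h after the first dose: D = ka/(ka − k) × [e^(−2k) − e^(−2ka)]
- Dilution: 1 − (mean or trough)/C(2)

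**Worked case, T = 6 h.** k = 0.1155, so ka/(ka − k) = 1.0909.

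- C(2) = 1.0909 × (0.7937/0.75 − 0.0625) = 1.086
- Mean = 1/(0.1155 × 12) = 0.721; ratio 0.721/1.086 = 0.66; dilution 34%
- C(12) = 1.0909 × 0.25/0.75 = 0.364; ratio 0.364/1.086 = 0.33; dilution 67%

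| Half-life (h) | Random time ÷ 2 h | Dilution | Trough ÷ 2 h | Dilution | Random time at steady state ÷ Day 1 at 2 h |
|---|---|---|---|---|---|
| 3 | 0.49 | 51% | 0.11 | 89% | 0.361/0.681 = 0.53 |
| 4 | 0.56 | 44% | 0.19 | 81% | 0.481/0.737 = 0.65 |
| 6 | 0.66 | 34% | 0.33 | 67% | 0.721/0.798 = 0.90 |
| 8 | 0.73 | 27% | 0.44 | 56% | 0.962/0.830 = 1.16 |
| 12 | 0.80 | 20% | 0.58 | 42% | 1.443/0.864 = 1.67 |
| 24 | 0.89 | 11% | 0.76 | 24% | 2.885/0.900 = 3.21 |

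The last column shows the shape over time. At half-lives up to 6 h an untimed late ECG sees, on average, less drug than the Day 1 tracing. From 8 h upward it sees more, so the series would rise from Day 1 and then drop somewhat from Days 4 and 7.

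**Sensitivity to time to peak.** With time to peak varied over 1 to 3 h and half-life over 2 to 24 h, the mean over the interval is 33% to 92% of the steady-state peak, which is 8% to 67% below it. The pairing of a 3 h peak with a 2 h half-life has no solution in this model and is left out.

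**Is steady state reached by the timed ECGs?** The share reached is 1 − 2^(−t/T). At the Day 4 morning dose (about 72 h) it is 1 − 2^(−6) = 98.4% for T = 12 h, higher for shorter half-lives, and 1 − 2^(−3) = 87.5% for T = 24 h. At Day 7 (144 h) it is 98.4% even for T = 24 h. A Day 7 visit held three days early still falls on Day 4.

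**The case against.** The strongest reply is that the timed ECGs already cover what matters. An effect that tracks concentration should show at 2 hours on Days 4 and 7, when steady state is nearly complete, and the protocol describes PK as time-independent over a week. A slowly accumulating effect depends less on being caught at 2 hours. This largely stands. It leaves two gaps: exposure that changes during weeks 2 to 4, and a delayed effect that still follows the peak.

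Three stronger readings are tempting, and the documents do not support them.

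- **That a concentration-related effect will appear to fade.** This depends on half-life, time to peak and when sites take the tracing, none of which is given. Any time includes 2 hours post-dose, and nothing ties the ECG to the pre-dose blood draw. With a long half-life the dilution is small and the series need not fall below its Day 1 level.
- **That steady-state peaks go unexamined.** Days 4 and 7 very likely sample close to steady state. That 2 hours is near the peak is itself an assumption.
- **That the comparison with placebo is biased.** Both blinded arms follow the same timing rule. Sensitivity falls, but neither arm is favoured by design.

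It is also fair to say that no ECG time-trend or concentration-ECG analysis is planned, so the risk lies in how a visit-by-visit summary is read rather than in a formal test. Section 5.5.4 already requires the exact dosing time in the eCRF, so half of what is needed to derive time since dose exists.

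**Conclusion.** The point holds in limited form. After the Day 7 visit no required ECG is tied to dose, for inpatients or discharged patients, and no planned analysis separates time on drug from time since dose. Late ECGs may therefore be less sensitive, and an apparent decline after Day 7 could not be told apart from a change in sampling time.

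The size cannot be settled from the documents. The 11% to 51% range rests on the assumed model and on untimed ECGs being spread evenly. The 24% to 89% range applies only if the tracing happens to coincide with trough. Both widen or narrow with half-life and time to peak. This is an inexpensive improvement to the design; it does not make the safety comparison invalid.

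**What to change.** In Section 8.11, Table 2 footnote l and Table 3 footnote k:

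1. Time the already scheduled inpatient Day 14 and Day 21 ECGs to 2 hours (±30 minutes) after the morning dose.
2. Apply the same timing to the Day 28 ECG when a morning dose is taken at that visit. With a ±3-day window and the last dose on Day 28, a visit on Days 29 to 31 has no dose to time from.
3. For every other ECG (discharge, early termination, Day 28 visits held after the last dose, missed timings), record the clock time of the tracing and derive time since last dose from the dose times already recorded. For discharged patients, confirm the time of the last self-administered dose at the visit.
4. State in the analysis text that timed and untimed tracings are summarized separately, and that visit trends are read from the timed ones.

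No ECG is added. Inpatient doses are given by center staff, so the timing is feasible. The cost is some scheduling freedom and, for discharged patients on Day 28, about one more hour on site beyond the existing 1-hour post-dose PK sample. Discharged patients have no Day 14 or Day 21 ECG in Table 3, so the timed series at those visits will describe those still in hospital and should be labelled so.
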